### **11.3. Criteria for Determining Relationship to Drug**

Assessment of causality of suspected AEs is based on associative connections (time or place), pharmacological explanations, previous knowledge of the drug, presence of characteristic clinical or pathological phenomena, exclusion of other causes, and absence of alternative explanations. The Investigator will be asked to assess the causal relationship to the study drug according to the following classifications:

- **Not related:** Time relationship with study drug administration is nonexistent or other factors, certain or probable, to have been causative.

- **Unlikely:** Time relationship with study drug administration is doubtful or other factors, certain or probable, to have been causative
- **Possible:** Time relationship with study drug administration may exist. Other possible causative factors may exist (e.g., concurrent disease or concomitant medication). Improvements on de-challenge or dose reduction (if performed) may or may not have been seen.
- **Probable:** Time relationship with study drug administration likely exists. No other possible causative factors may exist (not reasonably explained by the subject's known clinical state or concomitant medication). Improvements on de-challenge or dose reduction (if performed) have occurred. Recurrence of symptoms on re-challenge (if performed) has occurred. A specific laboratory investigation (if performed) has confirmed the relationship.
- **Definite:** Those events for which there is no shadow of doubt that they are a consequence of administration of the test product. It is likely that such events will be widely documented and generally accepted as having association with the test product or that they reoccurred after re-challenge (if performed).

#### 11.4. Adverse Event Reporting

All SAEs must be reported, whether or not considered attributable to the test product, on a separate SAE Report Form. As much information as possible should be supplied at the time of the initial report with at least the following information:

- Subject, treatment, and study identifiers;
- Investigator's name and Institution identifier (i.e., Sponsor site number);
- Description of the event, action taken, and outcome;
- Date and time of onset and current status;
- Any suspect (study or concomitant) drug, with its start date, dose, and form of administration; Reason the AE is regarded as serious; current assessment or opinion of causality; and
- Any other available diagnostic information that will contribute to the understanding of the event.

An initial written report should be submitted within 24 hours of the Investigator's awareness of the event, consisting of the SAE report form accompanied by the demographics, medical history, AE.

The IRB or EC will be notified in writing (e.g., facsimile) by the Investigator per hospital procedures, within the required time frame as specified of an SAE requiring an expedited IND safety report, in accordance with 21 CFR 312.32.

### 11.5. Definitions

A serious adverse event (SAE) or reaction is any untoward medical occurrence that at any dose:

- Results in death;
- Is life threatening (life threatening refers to an event in which the subject was at immediate risk of death at the time of the event; it does not refer to an event that hypothetically might have caused death if it were more severe);
- Requires inpatient hospitalization or prolongation of existing hospitalization;
- Results in persistent or significant disability or incapacity;
- Is a congenital anomaly or birth defect; or
- Is medically significant, and though not included in the above list, is an important medical event that may jeopardize the subject or require medical intervention to prevent one of the outcomes listed above. Discontinuation of study drug or conduct of additional diagnostic evaluations, will not, by themselves, satisfy the criterion for a medically significant event.

Medical judgment should be exercised in deciding whether expedited reporting is appropriate in other situations, such as important medical events that may not be immediately life threatening or result in death or hospitalization, but that may jeopardize the subject or may require intervention to prevent one of the other outcomes listed in the definition above. These events should also usually be considered serious. Examples of such events are intensive treatment in an emergency room or at home for allergic bronchospasm, blood dyscrasias, or convulsions that do not result in hospitalization, or development of drug dependency or drug abuse.

### 11.6. Follow-up of Adverse Events and Serious Adverse Events

The reporting period for adverse events is the period from signing the informed consent through 30 days after the last study drug administration. Adverse events/experiences will be followed until the event resolves or stabilizes and must be recorded on the AE eCRF. If clinically significant findings are present at study termination, a determination will be made about each persistent clinically significant finding. If not clinically important (i.e., does not pose a health risk to the subject) then follow-up will cease. If clinically important, additional follow-up will continue on a case-by-case basis until satisfactory resolution or resolution with sequelae is determined. Any SAE assessed as not related to study drug will be followed as clinically indicated until its resolution or, if not resolving, until considered stable or until the final study visit, whichever comes first. Any SAE assessed as related to study drug will be followed as clinically indicated until its resolution or resolution with sequelae is determined. Outcome may be classified as resolved, resolved with sequelae, continuing, fatal, or unknown (lost to follow-up).

#### Pregnancy

If a female subject becomes pregnant during the study, the Sponsor's Medical Monitor must be notified immediately. Although pregnancy is not considered an SAE, an abnormal outcome of pregnancy may lead to a SAE. Therefore, the SAE Report Form will be used to report the pregnancy of a female study participant to the Sponsor. Pregnancies must be followed until birth, termination of the pregnancy, or loss of subject follow-up.

## 12. STATISTICAL PLAN

### 12.1. Statistical Methods

This open-label extension study is designed to assess the safety, tolerability and efficacy of Cysteamine Bitartrate Delayed-release Capsules (RP103) for treatment of children with inherited mitochondrial disease.

The sample size will be up to 25 subjects (the maximum number of participants planned for study RP103-MITO-001).

Any interim analyses will be described in detail in the statistical analysis plan (SAP), which will be developed and specify the statistical methods to be used. The SAP will be finalized prior to data cutoff or database lock for the subsequent analysis. Demographic and disposition data, drug administration, medical history, prior and concomitant medications, AEs, clinical laboratory measurements, vital signs, ECG measurements, physical examination findings, and all other safety data will be listed by subject and timepoint. Descriptive statistics will be tabulated for change and shift from Baseline in the safety laboratory variables (serum chemistry, hematology, and urinalysis), vital signs, [score names] scores and ECGs. Adverse events will be summarized by method of collection type, frequency, severity, relationship to study drug, any change in study drug administration, and number of subjects per treatment. Safety laboratory values outside reference ranges will be flagged in laboratory listings.

AEs will be categorized using MedDRA, and listed by verbatim, primary term and SOC. SAEs will include MedDRA coding of primary and secondary (non-serious) event terms.

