Statistical Analyses:	
This extension study is designed to assess the efficacy, safety and tolerability of RP103 delayed-release cysteamine bitartrate capsules in patients with inherited mitochondrial disease.
 
The sample size will be up to 25 subjects (the maximum number of participants planned for Study RP103-MITO-001)
 
Any interim analyses will be described in detail in the statistical analysis plan (SAP), which will be developed and specify the statistical methods to be used. The SAP will be finalized prior to

	
data cutoff or database lock for the subsequent analysis. Demographic and disposition data, drug administration, medical history, prior and concomitant medications, adverse events, clinical laboratory measurements, vital signs, ECG measurements, physical examination findings, and all other safety data will be listed by subject and timepoint. Descriptive statistics will be tabulated for change and shift from Baseline in the safety laboratory variables (chemistry, hematology, urinalysis), vital signs and ECGs. Adverse events will be summarized by method of collection type, frequency, severity, relationship to study drug, any change in study drug administration, and number of subjects per treatment.
 
Adverse events will be categorized using MedDRA, and listed by verbatim, primary term and system organ class (SOC).

--	---

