### 6.1. Primary Objective

To assess safety, tolerability and efficacy of long-term repeat dosing of RP103 in children with inherited mitochondrial disease.

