### **4.6.2. Adverse Events**

Adverse events will be coded using the MedDRA (version 17.0) coding system and displayed in tables and data listings using system organ class (SOC) and preferred term (PT).

Analyses of AEs will be performed for those events that are considered treatment-emergent, where a treatment-emergent adverse event (TEAE) is defined as any AE with onset after Day 1 of drug administration. TEAEs will also be summarized. If the start date of an AE is partially or completely missing, the date will be compared as far as possible with the date of the start of administration of study drug. If the start date/time of an AE is partially or completely missing, the date/time will be compared as far as possible with the date/time of the start of administration of study drug. The AE will be assumed to be treatment emergent if it cannot be definitely shown that the AE did not occur or worsen during the treatment-emergent period (worst case approach). The following approach will be taken:

- If the start time of an AE is missing but the start date is complete, an AE will only be excluded as being treatment emergent if the start date is before the date of Day 1 study drug administration or if the stop date/time is before Day 1 study drug administration.
- If the start time and day are missing but the start month and year are complete, an AE will only be excluded as being treatment emergent if the start month/year is before the month/year of Day 1 study drug administration or if the stop date/time is before Day 1 study drug administration.
- If the start day and month are missing but the start year is complete, an AE will only be excluded as being treatment emergent if start year is before the year of Day 1 study drug administration or if the stop date/time is before Day 1 study drug administration.
- If the start date is completely missing, an AE will be considered treatment-emergent unless the stop date/time is before Day 1 study drug administration.

These imputations will be used for determining treatment emergence for adverse events; the unimputed partial dates will be included in the data listings.

Adverse events are summarized by subject incidence rates; therefore, in any tabulation, a subject contributes only once to the count for a given SOC or preferred term.

The number and percentage of patients with any treatment-emergent AE (TEAE) and with any related TEAE, with any Grade  $\geq 3$  TEAE, with any serious TEAE, and with any TEAE leading

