to withdrawal of study drug, and will be tabulated. In these tabulations, related is defined as any TEAE deemed possibly, probably or definitely related to study drug by the investigator.

Tabulations by SOC and PT will also be produced for all treatment-emergent AEs and for serious TEAEs, presented in alphabetical order by SOC and PT.

No formal hypothesis-testing analysis of adverse events incidence rates will be performed.

All adverse events occurring on study will be listed in subject data listings. By-subject listings also will be provided for the following: subject deaths; serious adverse events; and adverse events leading to treatment withdrawal or death.

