## **5. CHANGES TO PLANNED ANALYSES**

The study was closed prematurely and results will be summarized in an abbreviated clinical study report. Thus, certain analyses described in the protocol (all efficacy analyses, pharmacokinetic and pharmacodynamic analyses, analysis of seizure activity, summaries of AEs by severity, AEs by relationship to study drug, and AE method of collection) will not be performed.

6.

1

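### The SAP's adverse event tables count subjects only, so repeated episodes of the same term show only in the listings; an event count beside n (%) would put recurrence in the tables

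*Protocol*

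**What the plan says.** The primary objective in Protocol 6.1 is "To assess safety, tolerability and efficacy of long-term repeat dosing of RP103 in children with inherited mitochondrial disease".

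For the AE summaries, the Protocol Synopsis states "Adverse events will be summarized by method of collection type, frequency, severity" and continues as Protocol 12.1 does: "frequency, severity, relationship to study drug, any change in study drug administration, and number of subjects per treatment". Neither place defines frequency.

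SAP 4.6.2 sets the unit of analysis: "Adverse events are summarized by subject incidence rates". From this it derives the counting rule that "in any tabulation, a subject contributes only once to the count for a given SOC or preferred term". The overall table is in the same unit: "The number and percentage of patients with any treatment-emergent AE (TEAE) and with any related TEAE", followed by Grade 3 or higher, serious, and leading to withdrawal of study drug. Two SOC/PT tables follow, one for all treatment-emergent AEs (TEAEs) and one for serious TEAEs. No number of events is described for any of them.

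SAP Section 5 explains that the study closed early and that the report will be abbreviated, and it itemises what is dropped. For AEs the list reads "summaries of AEs by severity, AEs by relationship to study drug, and AE method of collection) will not be performed". Frequency is not on it.

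Event-level data are kept outside the tables: "All adverse events occurring on study will be listed in subject data listings" (SAP 4.6.2).

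**The concern.** The protocol sentence treats frequency and number of subjects as different things, and the SAP delivers only the second. Three neighbouring items from that sentence are openly dropped. Frequency is neither dropped nor visibly delivered as a count of events.

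This matters because of the question the study asks. The reactions that Protocol 5.3 calls most common include vomiting, abdominal pain, nausea and diarrhea, all of which can come and go over months of dosing. The checklist in Protocol 15.5 asks about each of them at every visit. A child with one recorded episode of vomiting and a child with many separate records each add one to the same cell. With the severity and relationship breakdowns also dropped, the SOC/PT tables carry most of the tabulated tolerability information, and they are silent on recurrence.

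**Working it through.** The plan states no figure to reproduce. The check is a comparison of texts, followed by an illustration on stated assumptions.

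**Step 1: the protocol's AE sentence, item by item, against the SAP.**

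| Item in Protocol 12.1 and Synopsis | In SAP 4.6.2 tables | In SAP Section 5 |
|---|---|---|
| Method of collection | none | declared dropped |
| Frequency | subject incidence only | not named |
| Severity | subjects with any Grade 3 or higher TEAE | declared dropped |
| Relationship | subjects with any related TEAE | declared dropped |
| Change in study drug administration | subjects with a TEAE leading to withdrawal of study drug | not named |
| Number of subjects | n and % | not named; delivered |

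**Step 2: what the counting rule does.** Let subject i have k(i) records of a given PT. The SAP cell is the number of subjects with k(i) ≥ 1. The number of events is the sum of the k(i). For any k(i) ≥ 1 the subject adds exactly 1 to the cell, so the tables carry no information on k(i) beyond whether it is zero. The by-subject listing shows all k(i) records.

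**Step 3: how much this could hide.** The documents give no event rates. The following are assumptions: Poisson recurrence at a common rate, two rates tenfold apart (0.5 and 5 recorded events per child-quarter), and follow-up of 2, 4 or 8 quarters. N is 25 (Protocol 12.3), and 8 quarters is the 24-month maximum (Protocol 7.5). Formulas: expected subjects counted = 25 × [1 − exp(−rate × quarters)]; expected events = 25 × rate × quarters.

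| Quarters | Subjects at 0.5 | Subjects at 5 | Ratio of subjects | Events at 0.5 | Events at 5 |
|---|---|---|---|---|---|
| 2 | 25 × (1 − e^−1) = 15.8 (63%) | 25.0 (100%) | 1/0.632 = 1.58 | 25 | 250 |
| 4 | 25 × (1 − e^−2) = 21.6 (86%) | 25.0 (100%) | 1/0.865 = 1.16 | 50 | 500 |
| 8 | 25 × (1 − e^−4) = 24.5 (98%) | 25.0 (100%) | 1/0.982 = 1.02 | 100 | 1,000 |

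The percentages are the same if N is the 35 of SAP 4.1. Because SAP 1.1 says the study closed early, the shorter rows are the more relevant ones. For a small product of rate and time, 1 − exp(−x) is close to x, so incidence then follows the event rate well and little is lost.

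**The case against.** **Recurrence is still on record.** A reader might infer that repeated intolerance cannot be seen at all. The documents do not support that. Every AE is listed by subject, and with at most 25 (Protocol) or 35 (SAP) children the listings can be read by hand. Tolerability also shows in TEAEs leading to withdrawal of study drug, in days with a missed dose (SAP 4.6.1) and in reasons for withdrawal (SAP 4.4). This stands, and it confines the point to the summary tables. It does not remove the point, because Protocol 12.1 plans both listings and summaries.

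**Frequency may mean incidence.** A reader might infer that the SAP breaks a clear protocol commitment. That also goes too far. The word is undefined, number of subjects per treatment could be the group size, and Protocol 12.1 leaves the methods to the SAP. Silence in Section 5 fits an author who thought frequency was delivered as incidence. The separate listing makes event counts the more natural reading, but not the only one.

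**The tables may hold more than the text describes.** The SAP's list of tables and listings (Section 6) is not in the available text, so the table shells cannot be checked. The counting rule is framed in terms of subject incidence and does not forbid an extra column. Still, it is written to apply in any tabulation, and no event column is described.

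**The illustration must not be over-read.** A reader might conclude that incidence nears 100% whatever the burden. The 2-quarter row (63% against 100%) shows otherwise, and the rates are assumed.

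**Event counts are imperfect.** The checklist records presence or absence since the last visit, and visits are quarterly. AEs already reported are updated and followed until they resolve or stabilise (Protocol 10.1.2 and 11.6). Recurrent vomiting may be one continuing record at one site and several at another. This stands as a real limit on the proposed column.

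**Convention.** Once-per-subject incidence is a normal way to present AEs, and the study is descriptive (SAP 4.2.5). That is true, and it is why the change proposed is an addition, not a replacement.

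**Conclusion.** The point holds in a limited form. On the natural reading of the protocol, frequency means event counts. The SAP tabulates subject incidence only and does not list frequency among the dropped summaries. Repeated episodes of the same term are therefore visible in the by-subject listings but in none of the AE summary tables that the SAP describes, which limits what those tables say about tolerability of long-term repeat dosing.

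The size of the loss is not determinable from the documents. In the illustration, a tenfold difference in event rate appears as a 1.58-fold difference in subjects at 2 quarters and 1.02-fold at 8. At low rates or short follow-up the loss is small. The conclusion rests on two assumptions: that frequency was meant as event counts, and that the unseen table list adds no event column. Even if frequency meant incidence, an event count would still be a cheap improvement to the tables serving the primary objective.

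**What to change.** In SAP 4.6.2:

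- Keep n (%) of subjects. Add the number of events (AE records) to the overall TEAE table and to the two SOC/PT tables (all TEAEs and serious TEAEs).
- Reword the once-per-subject rule so that it applies to the subject-count column only.
- Add a footnote saying that event counts depend on how sites split or merge intermittent symptoms into records, and that they are to be read descriptively alongside the listings.

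The cost is one column in tables already planned, built from AE records already collected, plus a sentence and a footnote in the SAP. No data collection or test changes. The downside is the record-splitting problem: without the footnote, differences in recording habit could be mistaken for differences in burden.

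Only noting in Section 5 that event counts are not tabulated would settle the wording, but it would leave recurrence out of the tables and so is not enough by itself.

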### 12.2. Analysis Set

All subjects who receive at least one dose of study drug (RP103) will be included in the safety analysis set. All subjects who complete all protocol-specified study visits with evaluable efficacy data will be included in the efficacy analysis sets.

### 12.3. Sample Size Considerations

The sample size will be up to 25 subjects (the maximum number of participants planned for study RP103-MITO-001).

### 12.4. Accountability Procedure

Missing values will not be imputed.

### 12.5. Termination Criteria

All ongoing enrolled subjects will continue to be dosed until subject withdrawal, or the Investigator withdraws the subject from the study.

### 12.6. Deviation Reporting

The following protocol deviations will be recorded and summarized in the final report: 1) eligibility (inclusion/exclusion) violations, 2) study drug dosing violations, 3) excluded medication violations, 4) procedures performed outside the protocol-specified window, 5) procedures not done, 6) subject non-compliance and 7) other, to be specified by the Investigator.

## 13. ADMINISTRATIVE ASPECTS

### 13.1. Change in Protocol

Unless absolutely necessary for safety of a patient, there will be no alterations in the protocol without prior agreement between the Sponsor's representative, the IRB/EC, and the Investigator. Protocol amendments will be submitted to Regulatory Authorities and to the Investigators for submission and reviewed by IRB/ECs and will not be implemented until regulatory and local (IRB/EC) approval are granted.

### 13.2. Disclosure

All information provided regarding the study, as well as all information collected/documentated during the course of the study will be regarded as confidential. The Investigator agrees not to disclose such information in any way without prior written permission from the Sponsor.

### 13.3. Monitoring

The Sponsor will designate a Sponsor's Study Monitor (i.e., clinical research associate) who will be responsible for monitoring this clinical trial. The Sponsor's Study Monitor will monitor the study conduct; ensure the proper completion and retention of source documentation, accurate study drug accountability records and prompt data entry to eCRF. To this end, the Sponsor's Study Monitor will visit the study site at suitable intervals and be in frequent contact through verbal and written communication (paper or email). It is essential that the Sponsor's Study Monitor have access to all documents (related to the study and the individual participants) at any time these are requested. In turn, the Sponsor's Study Monitor will adhere to all requirements for subject confidentiality as outlined in the Informed consent form (ICF). The Investigator(s) or their representative(s) will be expected to cooperate with the Sponsor's Study Monitor, to be available during a portion of the monitoring visit to answer questions, and to provide any missing information. Investigator(s) or their representative(s) are required to respond in writing to any deficiencies or action items documented by the monitor in the site visit follow-up documentation (which may be in the form of a trip report or letter or email). Appropriate investigator responses include written documentation (paper or email) of corrective or preventive actions, eCRF or source documentation corrections, training records, or Memos to File; such documentation should be placed in the investigator study file or patient research file/chart, as appropriate.

